## 5.3 Cost to the Subject

The device application is used via routine anesthesia service for given scheduled procedure. There is no additional cost to the study subjects.

## 4. Payment for Participation

Not applicable.

## 5.5 Return of Individual Research Results

Not applicable.

# 6. SAMPLE SIZE JUSTIFICATION AND DATA ANALYSIS

## 6.1 Sample Size Justification

The primary endpoint is the total length of desaturation episodes (ToLDE) time (in minutes) during a fixed 60-minute observation window during TIVA in patients with high risk of difficult airway management undergoing interventional radiology or GI procedures. Desaturation episodes are characterized by the occurrence of hypoxia (defined by  $\text{SpO}_2 \leq 92\%$ ).

A total of 120 eligible patients will be randomized in a 1:1 fashion using CORe. Blocking will be utilized to maintain exactly 60 patients per study group. The sample size is used to compensate for cases aborted post-randomization due to interventional radiology procedure changes interfering with the original treatment plan. This strategy will ensure that at least 50 patients are randomized and evaluable per study group.

For each study group, the ToLDE time will be summarized using the mean, standard deviation, median, and range. Interval estimation of the difference between study groups in mean ToLDE time will be computed with a 95% CI.

With at least 50 patients per group, the precision conferred on the bounds of a two-sided a 95% CI extends 0.39 units on each side of the observed mean assuming a common standard deviation of 1.0 per group (nQuery Advisor v7.0).

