### 3. STUDY DESIGN DESCRIPTION

This is a prospective randomized controlled study. Patients will be randomized in a 1:1 fashion to one of two study groups, the treatment group or control group. The patients in the treatment group will receive oxygen via Optiflow™ THRIVE; while the patients in the control group will receive 100% oxygen via a non-rebreather facemask. CORe will be used to conduct the randomization, as well as random block sizes; recommending to CORe that block sizes of 2, 4, 6, and 8 are allowable. Blocking will be utilized to maintain exactly 50 patients per study group. Patient randomization will occur after a patient has been deemed eligible and consented to participate. The data below listed will be collected during the procedure and statistically compared between the two groups at the end of the study.

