### 4. DISCUSSION OF SUBJECT POPULATION

#### 4.1 Subject Characteristics

- a) **Total number of subjects:** Due to lack of existing data to support a power analysis, the estimated number of study subjects is currently 120 eligible patients with 60 in each group. Due largely to the variation of caseload daily in IR, the average caseload for the study is expected no more than 2 cases/day. With the safety profiles in the previous reports mentioned above, the failure rate or the subject withdraw from the study is estimated no more than 1%.

All included cases will be scheduled elective procedures. Although we expect the rate of patient withdrawal to be low, we will not replace missing slots in the randomization list with the next eligible patient. Those patients will be considered randomized, but unevaluable. If needed, a protocol amendment will take place to increase the total number of randomized patients, only if this turns out to be an issue.

- b) **Study subjects:** Optiflow™ is a standard airway device used routinely and internationally, for high flow nasal oxygen (HFNO) delivery. Multiple studies have demonstrated that Optiflow™ is superior to the existing comparable devices in terms of both oxygenation and CO2 clearance. In addition, its safety profile in maintaining a patent airway is also superior to comparable devices during deep

sedation or general anesthesia (GA) without tracheal intubation. Standard anesthetic care will be provided to all patients with the exception of whether the patients receive HFNO or oxygen via non-rebreather face mask. Thus far, the literature has not demonstrated use in the pediatric population; patients < 18 years of age will not be included in this trial.

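### Sixty randomised per arm, without replacement and with no stated abort rate, makes 50 evaluable per arm likely only if post-randomisation loss is low; it does not ensure it

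*Combined protocol and SAP*

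**What the plan says.** Section 6.1 (Sample Size Justification) fixes the randomised number: "A total of 120 eligible patients will be randomized in a 1:1 fashion using CORe", and "Blocking will be utilized to maintain exactly 60 patients per study group". It gives the reason for going above 50: "The sample size is used to compensate for cases aborted post-randomization due to interventional radiology procedure changes interfering with the original treatment plan". It then concludes: "This strategy will ensure that at least 50 patients are randomized and evaluable per study group". The Brief Analysis Plan in the Summary Table has almost the same text. The precision statement that follows (a 95% interval extending 0.39 either side, with SD 1.0) is calculated at 50 per group, and Section 6.2 also assumes at least 50 per group.

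Section 4.1 (Subject Characteristics) deals with losses. It says that "we will not replace missing slots in the randomization list with the next eligible patient" and adds: "Those patients will be considered randomized, but unevaluable". It states that "the failure rate or the subject withdraw from the study is estimated no more than 1" per cent, and allows an amendment to raise the number randomised if losses become a problem.

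Section 3 sets the time of assignment: "Patient randomization will occur after a patient has been deemed eligible and consented to participate". It does not link assignment to confirmation of the procedure.

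**The concern.** A fixed number randomised, less a random number of losses that are not replaced, gives a random evaluable number. It can be said to ensure a minimum only if the loss rate is known and low. The plan gives no rate for the kind of loss that the margin is meant to cover.

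Two things are at stake. The first is whether a reader can rely on the stated evaluable size and the precision quoted from it. The second is the comparison itself. Each patient who is assigned and then dropped because the procedure changed is a post-randomisation exclusion. The plan expects such cases, and its timing rule allows them.

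**Working it through.** **Inputs.** Randomised per arm: 60 (Section 6.1). Evaluable target per arm: 50 (Section 6.1 and Summary Table). Replacement: none (Section 4.1). Post-randomisation abort rate: not stated, so it is treated below as an assumption *q* and shown over a range. SD: 1.0 and two-sided 95% interval (Section 6.1).

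**Step 1. Reproduce the plan's precision figure.** The half-width for a difference of two means is 1.96 × √(2/n). At n = 50 it is 1.96 × √(2/50) = 0.392, which matches 0.39. A single-group mean would give 1.96/√50 = 0.277. So the plan's figure belongs to the difference between groups, although the sentence refers to the observed mean.

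**Step 2. Find what the margin can absorb.** 60 − 50 = 10 patients per arm, and 10/60 = 16.7%. This is a tolerance. If 16.7% were also the true rate, the expected evaluable number would be 60 × 5/6 = 50, which leaves no reserve for chance variation.

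**Step 3. Probability of reaching 50.** Assume independent losses at the same rate *q* in each arm. The evaluable number per arm is then Binomial(60, 1 − q), and the probability that both arms reach 50 is [P(X ≥ 50)]².

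| Assumed loss *q* | One arm ≥ 50 | Both arms ≥ 50 |
|---|---|---|
| 1% | >0.999 | >0.999 |
| 5% | 0.9998 | 0.9997 |
| 10% | 0.966 | 0.933 |
| 12% | 0.901 | 0.811 |
| 15% | 0.716 | 0.513 |
| 16.7% | 0.583 | 0.340 |
| 20% | 0.323 | 0.105 |

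The probability for both arms stays at 95% or more only while *q* is about 9.5% or lower.

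**Step 4. Effect on precision.** 1.96 × √(2/n) gives 0.392 at n = 50, 0.413 at n = 45 and 0.438 at n = 40. Simulating both arms at 16.7% loss gives a median half-width of 0.392 and a 5th to 95th percentile range of 0.381 to 0.407. About 65% of such trials still round to 0.39 or better. At 20% loss the median is 0.400 and the 95th percentile 0.417.

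**Step 5. Check whether the 1% settles the matter.** At 1% total loss, 51 per arm would be enough (50/0.99 = 50.5). Section 6.1 takes 60, for a cause of loss that the 1% sentence does not mention. Section 4.1 ties the 1% to the device's safety record and describes it as failure or withdrawal. It does not clearly include aborted procedures.

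**The case against.** The strongest reply is that the margin may simply be generous. A reader might infer from the 10-in-60 cushion that the sponsor expects 16.7% loss, so that both arms would reach 50 in only about a third of such trials. The documents do not support that reading. They say what the margin is for and never give an expected rate. The only loss rate they state is 1%, at which the target is practically certain. This part of the reply stands: 0.34 is one point in a range and should not be presented as the expected result.

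The design also has a backstop, the amendment in Section 4.1. It is a genuine remedy, but it is reactive and has no stated trigger. By providing for it, the plan accepts that 60 might not be enough.

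A reader might also infer that the trial's precision is at risk. It is not, to any useful degree. The 0.39 is conditional on 50 per group, and even at 16.7% loss the half-width rarely exceeds about 0.41. This is a pilot without a power calculation.

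On timing, Section 3 does not say how long before the procedure assignment takes place. Section 5.1 selects patients from the daily schedule, so assignment may already be on the same day. Nor do the documents say whether the expected changes come before or after induction. A claim that later randomisation would remove all or most of the loss is therefore unsupported. So is a claim that losses would differ by arm, since the stated cause is a change of procedure. What remains is that Section 6.1 expects some cases to be lost after assignment, and Section 3 does not require the plan to be confirmed first.

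**Conclusion.** The guarantee in Section 6.1 and the Summary Table is unsupported. The plan's arithmetic is sound: 0.39 reproduces, and 60 × 5/6 = 50. The fault is that a conditional result is stated as a certainty and the condition, the abort rate, is missing. The probability that both arms reach 50 runs from near 1 at 5% loss to 0.10 at 20%, and the documents do not say where in that range the trial lies. The figures assume independent losses at a common rate in both arms.

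The consequence for precision is minor, about 0.02 SD units if each arm falls to 45. The more useful gain lies in avoiding exclusions after assignment, which a change of timing can reduce by an amount that cannot be calculated from the documents.

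**What to change.** 1. **Section 3.** Perform the CORe randomisation on the procedure day, after the interventional radiology procedure and the TIVA plan are confirmed and just before pre-induction oxygen starts. Cases changed before induction are then not randomised and later excluded. Changes after induction would remain. No extra patients are needed. The cost is that both devices must be at hand when the assignment is made.

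2. **Section 6.1 and the Summary Table.** Replace the guarantee with a conditional statement: the assumed post-randomisation loss rate with its basis, the resulting probability of at least 50 evaluable in both arms, and the half-width if fewer are evaluable. For illustration only, a 10% loss would read as about 93%, with half-widths of 0.39, 0.41 and 0.44 at 50, 45 and 40 per arm. The sponsor must supply the rate; 10% is not in the documents. This is a wording change, and its only cost is a slightly less favourable claim.

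With the same edit, state in Section 4.1 what shortfall would trigger the amendment and whether the 1% includes aborted procedures. Also reconcile the blocking target in Section 3 (50 per group) with that in Section 6.1 (60 per group).

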## 6.2 Planned Statistical Analysis

Descriptive statistics will be used to summarize continuous outcomes, and histograms and scatter plots will be used to explore the distributional characteristics and bivariate relationships, respectively. Transformations to the data will be applied if appropriate. Interval estimates will be computed for continuous variables, such as the mean number of hypoxemia (defined by  $\text{SpO}_2 \leq 92\%$ ) episodes within the pre-specified time period, for each study group (at least  $n = 50$ ) independently using a 2-sided 95% CI. Exploratory analyses between study groups will be conducted using t-tests (Wilcoxon rank-sum tests) for continuous covariates and chi-square tests (Fisher's exact tests) for categorical variables. Linear regression will be used to estimate the mean ToDLE time difference while adjusting for select covariates of interest.

## 7. METHODS AND STUDY PROCEDURES

Patients will be randomized into 1 of the 2 arms of the study, the intervention group and control group, by the use of randomizing software (CORe) to indicate which study group the patient has been assigned to. The patients in intervention group will be given 100% oxygen via Optiflow THRIVE with a flow rate of 50 L/minute for a period of 3 minutes prior to anesthetic induction and 70 L/minute thereafter anesthetic induction until the end of procedure; and the patients in control group will receive 100 % oxygen at the flow rate of 8 L/minute via a non-rebreather mask for 3 minutes prior to anesthetic induction and maintain the same flow rate until the end of procedure. The type of anesthesia for both groups will be total intravenous anesthesia (TIVA) without a tracheal intubation or super laryngeal airway support. The anesthesia for both groups will be induced with propofol boluses or continuous infusion. The dose of boluses or the infusion rate will be the decision of anesthesiologist. However, midazolam or fentanyl is generally avoided during the study to avoid the synergistic effects in respiratory depression. The quality of anesthesia (the depth and amnesia effect of anesthesia) is monitored by a BIS device with reading between 40-60, as satisfactory. The study coordinator will be responsible to follow the study procedures, to ensure the validity and integrity of the study protocol. The study coordinator will also be responsible for data collection when the 60-minute assessment window for monitoring begins. All data collection will take place prior to, and during, the patient's scheduled IR procedure. The 60-minute assessment window will begin after induction (initial Propofol administration; bolus), once induction has been recorded in the patient's electronic medical record via online time stamping in EPIC, and will conclude 60-minutes after (the recorded time of induction). Total length of desaturation episode(s) (ToLDE) will be recorded by utilizing a stop-watch/clock. All other collected data will be recorded via observation and patient monitoring during the procedure. The following data will be collected during the procedure and statistically compared between two study groups after completion of data collection (see **Appendix A.**):

1. Patient's demographic information
2. Patients underline diagnosis and ASA Physical Status
3. Procedure data, name, duration and position
4. Episodes and percentage duration of oxygen desaturation defined by  $\text{SpO}_2 \leq 92\%$  over the entire procedure
5. Episodes of manual airway support, including jaw thrust, or insertion of an artificial airway device
6. Episodes and duration of BIS number  $\geq 61$  during the entire procedure
7. Episodes of patient movement during the procedure
8. The total dose of propofol used during the entire procedure
9. Patient satisfaction after the procedure by post PACU discharge evaluation (see **Appendix B.**)

**Preoperative care:** No active intervention is planned on this phase of care. All procedures will be provided according to routine clinical care and clinical judgment.

**Intraoperative care:** Total intravenous anesthesia (TIVA) will be delivered using an intravenous infusion of propofol according to anesthesiologist clinical judgment. Intraoperative hemodynamic and temperature will be monitored and maintained according to routine clinical care. A BIS monitor measures the depth of anesthesia with reading between 40-60, as satisfactory.

**Postoperative care:** All patients will be monitored in PACU according to routine clinical care. If deemed necessary by the attending anesthesiologist, patients will be transferred to the intensive care unit.

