Exclusion Criteria	A patient who meets any of the following will be excluded from the study: 1. Has a significant pulmonary disease requiring supplemental oxygen in daily life (severe pulmonary fibrosis, severe COPD, etc.) 2. Has significant cardiac disease (including history of myocardial infarction (MI) with concurrent evidence of ischemic myocardial damage at the event, cardiomyopathy with impaired left ventricular ejection fraction to less than 50% or uncompensated congestive heart failure (CHF) 3. Cannot tolerate TIVA or having a proposed procedure without TIVA 4. Requires endotracheal intubation 5. American Society of Anesthesiologists (ASA) classification 5 6. Non-English speaking 7. Requires an emergency procedure
Outcome(s)/Endpoint(s)	The primary endpoint is the total length of desaturation episodes (ToLDE) time (in minutes) during a fixed 60-minute observation window during TIVA in patients with high risk of difficult airway management. Desaturation episodes are characterized by the occurrence of hypoxia (defined by $\text{SpO}_2 \leq 92\%$ ).
Study Procedures	
Pretreatment Evaluation	Routine preoperative interview and physical evaluation. No special evaluation required.
On-Study Visits	Onsite data collection in all the study patients including: 1. FDA approved Intervention group: patients receiving Optiflow™ THRIVE 2. Standard of Care group: patients receiving non-rebreather mask  Each patient will be followed for 60 minutes (from induction until 60 minutes thereafter).
Follow-up Visits	Per standard post-anesthesia care unit (PACU) discharge protocol
End of Study Visit	Per standard PACU discharge protocol

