### 9.1 Adverse Events Definitions

An adverse event (AE) is any undesirable clinical event occurring to the subject during a clinical study, whether or not it is considered related to the investigational product. This includes a change in a subject's condition or laboratory results, which has or could have a deleterious effect on the subject's health or well-being. An Adverse Event that is related to the investigational device may be referred to as an Adverse Device Effect (ADE). If any of the above-mentioned events occurs, the study will be terminated and case will report according to the standard clinical pathway.

An adverse event does not include:

- Medical or surgical procedures; the condition that leads to the procedure is not an adverse event
- Pre-existing disease, conditions, or laboratory abnormalities present at the start of the study that do not worsen in frequency or intensity
- Situations where an untoward medical occurrence has not occurred (e.g., hospitalizations for cosmetic or elective surgery or social/convenience admissions)
- Expected post-operative course

**Unanticipated Adverse Device Effect (UADE):** Any device related adverse event, the nature or severity of which is not consistent with or listed in the applicable product information (e.g., instructions for use, subject informed consent document, subject information brochure [if applicable], promotional literature) or any other unanticipated serious problem associated with a device that relates to the rights, safety, or welfare of subjects.

A serious adverse event (SAE) is defined as any adverse medical experience that results in any of the following outcomes:

- Death;
- Is life threatening;
- Requires inpatient hospitalization or prolongation of existing hospitalization;
- Results in persistent or significant disability/incapacity;

- Requires medical/surgical intervention to prevent permanent impairment or damage

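### The protocol gives conflicting end points for data collection and no end for the adverse-event period, so post-procedure harms may be recorded incompletely and inconsistently

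*Combined protocol and SAP*

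**What the plan says.** Text that closes collection early:

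- Section 7: "All data collection will take place prior to, and during, the patient's scheduled IR procedure". Apart from the stop-watch measure of the primary endpoint, it adds: "All other collected data will be recorded via observation and patient monitoring during the procedure".
- Summary Table, On-Study Visits: "Each patient will be followed for 60 minutes (from induction until 60 minutes thereafter").

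Text that reaches further:

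- Summary Table, End of Study Visit: "Per standard PACU discharge protocol". The Follow-up Visits row says the same in substance.
- Section 7, item 9: "Patient satisfaction after the procedure by post PACU discharge evaluation".
- Section 9.2 asks for all adverse events to be documented, including those the patient reports or is asked about. It states no time limit.
- Section 9.3 has the PI record all serious events in the study period. No section says when that period starts or ends.

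On the events themselves, Section 7 (Postoperative care) provides that, if the attending anesthesiologist finds it necessary, "patients will be transferred to the intensive care unit". None of items 1 to 9 records this. Two of the five SAE criteria in Section 9.1 are "Requires inpatient hospitalization or prolongation of existing hospitalization" and "Results in persistent or significant disability/incapacity".

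Three further statements narrow collection. The opening of Section 9 leaves events unrelated to the devices out of the study data, with the PI judging relatedness. Section 9.1 says the study will be terminated if one of the events it describes occurs. Section 10.2 ends data collection when an adverse event is identified. Section 6 plans no analysis of adverse events.

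**The concern.** A coordinator who follows Section 7 to the letter would make no study record of anything that happens in recovery. One who follows Section 9.2 would record it if told of it. Both would be complying with the protocol. What is recorded after the procedure then depends on who notices an event, who reports it, and how the PI judges relatedness. The document describes no blinding, so these steps can differ between arms.

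This matters because the pilot is meant to support planning of later studies (Section 1), and Section 10.3 expects its data to inform airway safety. The patients are selected for airway risk. A count of recovery-phase events gathered without a defined window or source would be hard to interpret in either arm, and harder to compare between arms.

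**Working it through.** **1. The plan's own precision figure.** Inputs from Section 6.1: 50 per group, common SD 1.0, two-sided 95% interval. Half-width for the difference in means = 1.96 × 1.0 × √(1/50 + 1/50) = 1.96 × 0.2 = 0.392, which reproduces the stated 0.39. It concerns the primary endpoint only, so a defined safety window changes neither this figure nor the total of 120.

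**2. When does collection end?**

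| Place | Implied end |
|---|---|
| Section 7, collection sentence | End of procedure |
| Summary Table, On-Study Visits | 60 minutes after induction |
| Section 7, items 4, 6 and 8 | Whole procedure, whatever its length |
| Summary Table, End of Study Visit | PACU discharge |
| Section 7, item 9 | After PACU discharge |
| Section 9.2 | None stated |
| Section 9.3 | End of an undefined study period |

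The 60 minutes is explained by Section 7 as the assessment window for the primary endpoint. The other rows cannot all be true of one collection period. In particular, item 9 cannot be obtained under the Section 7 sentence.

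**3. Which SAE criteria are affected?** Section 9.1 lists five. Death, a life-threatening event, and intervention to prevent permanent impairment can all occur during the procedure. Hospitalization or its prolongation, and persistent disability, are outcomes. The event that leads to them may begin during the procedure, but whether the criterion is met is usually known only later. So for two of five criteria, classification usually needs information from after the procedure.

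**4. Trace one event.** Take an unplanned ICU transfer from PACU.

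- Under the Section 7 sentence it is outside collection.
- Under items 1 to 9 it has no entry.
- Under 9.2 it is documented if someone observes or reports it as an adverse event.
- Under 9.3 it is recorded if it is serious and falls in the study period, which cannot be determined.
- Under the opening of Section 9 it leaves the study data if judged unrelated to the device.
- Under 10.2, data collection stops once an adverse event is identified.

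The same event is recorded or not according to which section is applied.

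**5. What a zero count would mean.** With zero events in n patients, the one-sided 95% upper bound is 1 − 0.05^(1/n): 5.8% for n = 50 and 4.9% for n = 60. The documents give no event rates. At assumed true rates of 1%, 2% and 5%, the chance of at least one event in 60 patients, 1 − (1 − p)^60, is 45%, 70% and 95%. All these figures assume that every event is recorded. If only a fraction c is recorded, a zero count bounds c × p rather than p, and the bound on p becomes 4.9%/c. Here c is unknown and may differ by arm. This is context only and does not show that any event is missed.

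**The case against.** The strongest reply is that the Section 7 sentence is being read too literally. It sits among the coordinator's duties for the assessment window and introduces a list of mainly intraoperative measures. Item 9 shows that it was not meant as an absolute cut-off. Section 9.2 covers events that patients report, which a patient under anesthesia cannot do, so it must reach past the procedure. Section 11.3 adds sponsor review for adverse events against source documents. The Summary Table places its follow-up and end-of-study rows under study procedures, which suggests that participation runs to PACU discharge. The CRFs in Appendix A are not shown, so they may hold fields that the text does not mention.

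Most of this stands, and it rules out a stronger reading that a reader might infer: that serious events after the procedure are missed by design. Under Sections 9.2 and 9.3 a postoperative event can be recorded. Three arguments for that reading also fail:

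- That the serious events defined in 9.1 all come afterwards. Three of the five criteria can be met during the procedure, and onset is not the same as outcome.
- That the background's cited study of early postoperative desaturation and discharge destination places the relevant harm outside the window. Its title in the reference list locates the desaturation in the operating theatre, and the study itself is not available here.
- That the trial will report a near-empty harms table. Section 6 plans no such table, and no rates are given.

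What the reply does not remove is the conflict in the text. Section 9 sets no end point, no scheduled post-procedure check and no source to consult, so capture is passive. The narrowing statements in Sections 9, 9.1 and 10.2 remain, and ICU transfer is absent from the list.

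**Conclusion.** The point holds as a contradiction and an undefined period. The protocol does not settle when collection ends, never defines the study period for adverse events, and foresees ICU transfer without listing it as data. Post-procedure harms may therefore be captured incompletely and inconsistently.

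The size cannot be estimated, because neither event rates nor the completeness of passive reporting is given. What can be said is that two of five SAE criteria usually need later information, and that the 4.9% to 5.8% bound from a zero count would apply only to events the recording can detect. The primary endpoint and its 0.39 precision are untouched.

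The conclusion assumes that the unseen CRFs and Adverse Event Form do not resolve the matter. If they define the window and record ICU transfer, the correction reduces to aligning the protocol text. The change should be made, but it does not threaten the primary comparison.

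**What to change.** 1. **Section 7.** Limit the collection sentence, and the one on observation during the procedure, to items 1 to 8. State that item 9 is obtained after PACU discharge. In the Summary Table, label the 60 minutes as the window for the primary endpoint.
2. **Section 9.3.** Define the study period, identically for both arms, as the start of preoxygenation to PACU discharge. State that unplanned ICU transfer, unplanned admission or prolonged stay, and death are taken from the medical record at discharge from the index encounter.
3. **Data list and Section 6.2.** Add unplanned ICU transfer and SAEs to the listed items, and summarize them by arm.
4. **Safety text.** Reconcile the opening of Section 9 (events unrelated to the device not collected) and Sections 9.1 and 10.2 (study or data collection terminated when an event occurs) with the recording duties in 9.2 and 9.3. Without this step the new items could still drop out.

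Desaturation in PACU could be added as a data item, but this is optional: the allocated oxygen delivery ends with the procedure, and the primary objective concerns performance during TIVA.

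The cost is protocol wording, a few CRF fields filled from existing records, and a little more abstraction time for the coordinator. There is no extra visit and no change to the 120 patients or to the 0.39.
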